- *Please see supplementary notes for applicants (at the end of this application form) for guidance on completing the research ethics application form*

- *Please note that a favourable opinion from the HSSD Research Ethics Committee does not constitute permission to carry out a research project. A favourable opinion means that the HSSD Research Ethics Committee is satisfied that ethical issues in planning the research project have been addressed to the satisfaction of the committee. Permission to carry out research still has to be obtained from the research site and department head.*
- *Please note that research being undertaken as part of an academic programme of study can only be granted HSSD Research Ethics approval pending a favourable opinion being granted by the university faculty REC. A record of this will need to be forwarded to the HSSD REC prior to commencing the research project in Jersey.*

Health & Social Services Department Research Ethics Committee

Applicant's Checklist

Title of Study:	Differential contributions of stress and pain-explicit mindfulness treatment groups to processes, patient experience and outcomes in chronic pain. A randomized controlled trial and qualitative analysis
Lead researcher:	[name]

- **This document MUST be completed and submitted as part of the application form. Please ensure ONE copy of each document, as detailed below, is attached as an appendix to this application form in the order that they appear on the list. ALL appendices MUST have dates and version numbers clearly marked.**

- **Indicate 'yes/no' as applicable, and continue your document list on a separate continuation sheet if necessary.**

Document	Enclosed?	Appendix №	Version №	Date
Applicant's Checklist (this form)	Mandatory			
HSSD Research Ethics application form	Mandatory			
List of references (APA format)	Mandatory	1		
Summary C.V. for lead researcher	Mandatory	2		
Letter(s) of invitation to participants/ Advert	Y  / N 	3		
Participant Information Sheet(s)	Y  / N 	4		
Participant and treatment provider consent form(s)	Y  / N 	5		
Course facilitators conent form	Y  / N 			

If the proposed research is sponsored by a pharmaceutical company, has that company agreed to abide by:

- I. The Association of the British Pharmaceutical Industry Guidance on Insurance and compensation in the event of injury in Phase 1 clinical trials 2012 (patient studies)?

Yes No

- II. The Association of the British Pharmaceutical Industry Guidelines for Phase 1 Clinical Trials

2012?

Yes

No

7. Good research practice:

Please confirm that the research will be carried out in accordance with the 4 Ethical Principles of Research – autonomy, beneficence, non-malficence and justice and in accordance with recognised standards of practice as in the Declaration of Helsinki

I agree to undertake the proposed research, as outlined in this application, in accordance with the 4 Ethical Principles of Research and the Declaration of Helsinki.

Please state which other professional codes of conduct you will abide by (if applicable):

Type your statement of practice here

8. Will you require ethical opinion from another source?

Yes

No

If Yes, which other ethics committee approval do you require? i.e. university faculty REC, MREC etc.

Part 3: The research

1. Type of research proposed:

Please indicate whether the proposed research is:

Quantitative

Qualitative

Both

If other please detail:

2. Outline of the research:

Please provide a brief outline of the proposed research under the sub-headings below.

N.B. below we included a scientific and lay person abstracts for your assistance as by way of introducing the project briefly.

200-word lay abstract

Mindfulness is a popular set of knowledge and practical techniques that can help people cope with stress. It includes meditation practices, everyday small practices to break and change usual habits, as well as understanding and developing competencies to be more aware of thoughts, emotions and physical sensations. Mindfulness can help not to excessively react to them, or becoming distressed by them.

In persistent pain (pain that lasts more than three months), mindfulness is thought to improve depression, quality of life, and even how sore people feel.

There are numerous versions of mindfulness and mindfulness-based therapies. One approach, Acceptance and Commitment Therapy (ACT), is based on science (as opposed to religion or common sense). ACT helps people to learn about and apply skills to cope with thoughts, emotions and sensations without getting upset, distracted or impeded by them. It also assists people to develop the ability to set clear goals that matter in their life. ACT evaluates successful outcomes in this areas (called 'processes') and how they link to changes in pain, mood and stress. However, more puritan mindfulness courses tend to only focus on the latter.

Research on mindfulness courses for chronic pain, can show that people improve, but not so well what changes in people's experience and skills, or how they apply these. We also know that pain sufferers who attend mindfulness courses for stress, may say it is not so relevant to their pain difficulties.

In this study we want to explore how both mindfulness for stress and mindfulness for pain courses, online, contribute to:

- how specific areas of ACT and other mindfulness learning change

If/how these link with practical skills and any emotional or improvements in the participants' quality of life, use of medication or GP visits. To help us evaluate this, we will ask participants to complete scientifically accepted questionnaires and interview them. We will then use statistical methods and qualitative methods to evaluate change.

This may help us with better supporting chronic pain sufferers with choices around mindfulness as a standalone or as part of attending intensive pain-coping programmes involving different professions.

Scientific abstract of the work proposed

In chronic (persistent) pain, mindfulness can improve coping, depression, quality of life, and reduce pain intensity. Both Acceptance and Commitment Therapy (ACT; Hayes, Strosahl et al. 1999) and mindfulness research, including Mindfulness Based Stress Reduction (MBSR, Kabat-Zinn 1982) and Mindfulness Based Cognitive Therapy (MBCT, Segal, Williams et al. 2002) provide theoretical and/or practical frameworks for *mindful* process measurement.

However, numerous methodological and contextual limitations exist within the context of pain management centres that are increasingly providing mindfulness based interventions to pain sufferers. This has potential implications for whether implementing mindfulness skills is done with clarity, good governance about whether, where and how it is helpful, or whether it even can be harmful, duplicate other treatments or unnecessarily burden pain sufferers with something that is not needed. In this context, it also has significant implications on any required development of teachers' competencies.

No current research has attempted to unify ACT and other mindfulness process measurement (how people get to change – as opposed to what change they achieve) or to establish the potential contribution and relevance of different specific mindfulness courses in chronic pain patients' treatment pathways and outcomes.

A community-based multidisciplinary-pain-management naïve sample (N=100) of chronic pain patients will be recruited in primary care and placed on a time-set waiting list and then randomly allocated to **one** of two standardised active online mindfulness treatments - stress **or** pain group

conditions. Measurement will include theoretically validated process and outcome measurement. Treatment adherence and fidelity will be independently evaluated from recorded sessions and inter-rater agreement checks performed.

Quantitative analysis will be performed to include descriptive statistics, analysis of variance, session-by-session process change trends, and post-hoc analysis on GP and A&E visits.

Qualitative thematic analysis will complement and bolster the findings of the quantitative phase to include additional process variables unaccounted for by the ACT model, patient experience and descriptive comparison of the two active conditions, including descriptive statistics comparing frequency of reported themes between the two treatments.

i. Aims and objectives:

This study aims to explore and better understand the contribution of standardised group-based mindfulness courses to theoretically valid and coherent mindful-change processes.

OBJECTIVES

1. To explore the differential contribution of standardised stress and pain-explicit group-based mindfulness courses on mindful-change process as described in the Acceptance and Commitment Therapy (ACT) psychological flexibility model (Hayes, Strosahl et al. 1999) on a chronic pain population that is naïve to multidisciplinary pain treatment.
2. To improve on methodological and confounding issues inherent in current research on mindfulness for chronic pain.
3. To contribute to the understanding of the potential relevance and role of standardised stress and pain explicit mindfulness courses in chronic pain treatment outcomes and pathways.

a. Hypotheses and/or research question(s) to be addressed:

Quantitative project

What is the differential contribution of online stress and pain explicit mindfulness courses to mindful-change process variables and outcomes? More specifically:

What individual contribution do mindfulness for stress (MfS; Hennessy 2017) and Mindfulness for Health – Mindfulness Based Pain Management (MfH-MBPM; Burch and Penman 2013) courses make to Acceptance and Commitment Therapy (ACT) processes and relevant chronic pain outcomes in pain-management-naïve chronic pain sufferers?

Which associations exist between weekly course content and specific process change?

Qualitative project

Given consideration of:

- a) The practical impossibility of quantitatively measuring all the relevant process variables,
- b) The potential questionnaire burden, and
- c) The sheer number of processes and mechanisms contained within both ACT and chronic pain literature on mindfulness courses and meditation,

[figure not shown]
we aim to utilise thematic analysis to complement the quantitative findings. This will allow us to explore the impact of both versions of courses, reduce questionnaire burden in the quantitative analysis, and contribute to answering the following questions.

- a) Which relevant ACT-process variables are reported by participants and how have they changed?
- b) Do participants report the presence of other contributing variables considered within the mindfulness-groups literature in chronic pain, such as group cohesion, engagement and the impact of teachers' experience on reported change?
- c) How frequently are these variables reported across the two groups, and in which direction? (improvement/deterioration/no change). This component will take the form of descriptive statistics and qualitative comparison of occurrence within patients' interview-derived themes.

ii. **Rationale, to include a *brief* synopsis of the background to the research:**

Mindfulness can be defined operationally as *Paying attention; on purpose in the present moment and non-judgmentally* (Kabat-Zinn 2013)

Evidence-based (often referred to as ‘secular’) mindfulness has seen an exponentially increasing interest in the scientific literature and the estimated number of published scientific journals has recently been reported to have grown from one single journal in 1982, to 667 scientific publications in 2016 (Kabat-Zinn 2017) and in excess of 30,000 Media Pieces in Newspapers (Van Dam, van Vugt et al. 2018)

(extract from Kabat-Zinn 2017)

However, there are unknowns around the mechanisms (the ‘vehicles’ of change) by which mindfulness works, and that these must be understood in order to avoid continued professional and public misinformation, poor research and ultimately, potential harm to the end user. (Van Dam, van Vugt et al. 2018).

ISSUES WITH AND IMPLICATIONS OF WHAT WE CURRENTLY DEFINE AS MINDFULNESS AND ITS APPLICATION TO CHRONIC PAIN

Within the context of the exponential growth of interest in and research of mindfulness (e.g. Kabat-Zinn 2017, Van Dam, van Vugt et al. 2018) including in the treatment of chronic pain (Bawa, Mercer et al. 2015, Hilton, Hempel et al. 2017), several factors have contributed to the consideration for the current project:

1. The integration of mindfulness based interventions in gold-standard multidisciplinary treatments for chronic pain, such as ACT (BPS 2013),
2. Researchers' calls to improve intention to treat, to better understand facets of what is understood to be mindfulness, better targetting of and a more unified approach to mindfulness-change process variables – thus aiming to reduce treatment burden.
3. There are relevant mindful mechanisms and processes specifically in chronic pain that have made a case from both the ACT and the more purist mindfulness research derived from group based interventions or meditation alone in chronic pain – and that are not currently typically or routinely included in mindfulness groups research for chronic pain.
4. Methodological issues including
 - a. lack of clarity about providers' competencies and requirements in chronic pain,
 - b. arbitrary removal of essential components of a given intervention,
 - c. often no active or waiting list control condition and
 - d. no consideration at all of utilising a theoretically valid and coherent process-measurement frameworks nor consideration for the teachers' competencies requirements when delivering mindfulness courses to chronic pain patients

(e.g. Dobkin 2008, Day, Jensen et al. 2014, Van Dam, Hobkirk et al. 2014, Day 2017, Harrison, Scott et al. 2017, Hilton, Hempel et al. 2017).

From reviewing the evidence quoted, the research on mindfulness for chronic pain has exclusively utilised standardised mindfulness groups typically aimed at stress populations, excluded less researched pain explicit (contextually relevant to pain) mindfulness group interventions, ignored theoretically valid mindful-process measurement provided by the ACT framework, or not controlled appropriately for significant counfounding factors.

This debate is increasingly important considering that recently published audit data suggests that

mindfulness in one format or the other, or as part of ACT-based multidisciplinary treatment is being provided regularly in pain management centres in the UK . This has been leading, possibly prematurely, to discussion about providing training in mindfulness competencies for pain practitioners such as mindfulness enquiry or leading meditations (e.g. Williams, Watson et al. 2017), which may lead, in turn, to implementing professional skills without sound, targeted and theoretically evidenced rationale.

METHODOLOGICAL ISSUES WITH CURRENT MINDFULNESS RESEARCH AND THE IMPROVEMENTS WITH THIS STUDY

The current research will therefore aim to address and control, some of the currently reported methodological issues in research on group mindfulness based interventions (MBIs), including:

- Utilising a waiting list for the whole group as a control prior to randomisation. This will act as a pseudo treatment-as-usual condition and will track key outcome and process measures across this time.
- Utilising two active interventions, Mfs and MfH-MBPM, with standardised, transparent, comparable in content, time and delivery process that can therefore be easily evaluated for adherence and treatment fidelity.
- Using established and matched teacher's competence in line with UK Network standards (MBTT 2011)for the intervention delivered.
- Utilising the same 'dosage' and type of interventions (groups with similar structure, delivery times and requirements for practice) utilising MfH-MBPM and MfS (Burch and Penman 2013, Hennessy 2017)
- Using appropriate psychometric and qualitative analysis and targetting of explicit process-change.
- Reporting adverse side effects
- Measures in line with IMMPACT recommendations for research on chronic pain (Dworking *et al.*, 2005).

iii. **Study design, to include recruitment and sampling strategy, inclusion/exclusion criteria, sample size and justification:**

In order to address the research questions, the current study will be divided in and presented as separate quantitative and qualitative components:

Quantitative study:

Design and Method

DESIGN

A waiting-list controlled, randomised, pilot trial of mindfulness based group treatment comparing two active standardised interventions (mindfulness for stress vs. mindfulness for pain/health)

SETTING AND STUDY POPULATION

An opportunity sample via general practice, waiting-room advert and GP supported recruitment in Jersey, serving a population of 106,000, will be invited to take part in the study.

RECRUITMENT

All general practices in Jersey will be invited to take part in this study. They will be recruited through the Jersey Primary Care Body and Social Media Advertising.

CASE IDENTIFICATION

Over a six months period.

Once potential participants have consented, searches will be run on GP electronic health records to identify suitability. Demographic data including gender, age, ethnicity and employment status, pain diagnoses, current medication and dosage, co-morbidities and mental health diagnoses will be extracted via GP referral to the study, including that the patients meet inclusion criteria and do not meet any of the exclusions.

INCLUSION AND EXCLUSION CRITERIA (PATIENTS)

Inclusion criteria:

1. Pain > 3 months
2. Ability to communicate and literacy in English
3. Age 18 years or older
4. No current outstanding medical tests or procedures for conditions expected by the GP to interfere with participation in treatment.
5. Has not previously received non-medical treatment at a specialist pain centre, or

attended a multidisciplinary pain management programme.

6. Ability to utilise online video conferencing technology (i.e. ownership of a compatible device & necessary technical competence)

Exclusion criteria:

7. Patients who are actively suicidal, terminally ill or have dementia, cognitive impairment, learning difficulties, or the GP knows of another reason to exclude.

ETHICAL ISSUES

Informed consent

We will obtain approval to contact practices regarding the study with participant's information leaflet and GP information leaflet. We will also obtain informed consent from the treatment providers, including in relation to video/audio feed being recorded. Participants will be offered opportunity to switch off their cameras.

Confidentiality

Data will not be accessed outside the research team. Once collected, checked for inclusion criteria and allocated to a randomly generated participant number, data will be anonymised and prior to the off-site transfer for blind analysis (the statistician will not be aware of which condition stress/pain the participants have been allocated to). Data Transfer Protocols will be utilised in line with the Government of Jersey Governance and Data Protection system, to transfer the data ahead of analysis.

A participant waiting-list randomised, pilot trial of mindfulness based group treatment comparing two active interventions (stress vs pain mindfulness courses) and the waiting-list at recruitment time and 8-weeks post recruitment, coinciding with the start of treatment.

Randomisation will be based on computer-generated random numbers and the sample randomised, will act as a pseudo-waiting-list control for the eight-week waiting period ahead of the intervention.

Recruitment details and Participants

PARTICIPANTS AND DATA COLLECTION

100 people with chronic pain (defined as > three months duration) will be recruited from primary care and social media adverts in Jersey (the social media participants will be

required to register their interest via their GP who will then refer to the lead researcher). Once recruited, participants will be required to complete baseline outcome and process measures, 8-weeks ahead of beginning their 8-week course. Randomisation will take place at this point to either the stress or the pain course. They will repeat this assessment on week 1 of the course and then again at week 4. They will also complete only process measures weekly during the course, in order to explore for links between weekly course content and specific process change.

Posttreatment assessment will be completed within four weeks of treatment completion and at 3-month follow up.

How this study will improve on previous research

The current study therefore offers an opportunity to impact on the understanding, application of mindfulness and management of chronic pain in the following ways:

- Improved targeting of mindfulness courses as part of multidisciplinary treatment for chronic pain
- A better understanding of the contribution that mindfulness courses may provide in chronic pain patient treatment pathways, as improved understanding of their mindful-process-change relevance, may allow improved targeting and avoid unnecessary duplication, treatment burden or even harm.
- Improving the understanding of the requirement for and development of relevant teaching/training competencies in mindfulness in this area.
- Potentially contributing to establishing whether full mindfulness courses have a place (and what that is) building up to, or as part of multidisciplinary pain management programmes or possibly ahead of these, within the community or as an adjunct to them- for chronic pain sufferers.

Procedure:

100 people with chronic pain (defined as > three months duration) will be recruited from primary care and social media adverts in Jersey (the social media participants will be required to register their interest via their GP). The allocation (stress or pain) will not be concealed from the participants, treatment providers or the researcher. However, analysis of the data will be conducted blind to allocation. Post-treatment assessment will be completed within four weeks of

treatment completion and at 3-month follow up. The sample size has been determined to recruit 8-12 participants for each of four stress and pain courses to be administered with a recruitment of 50 and a minimum target of 30 per active intervention.

Qualitative study:

DESIGN AND SETTING

A qualitative study involving semi-structured interviews will be held, with a topic guide informed by the ACT psychological flexibility model (Hayes, Strosahl et al. 1999) and Day's framework for mindfulness-relevant processes (Day, Jensen et al. 2014) in chronic pain, and based on mindfulness research improvement based on adaptations of Mindfulness Based Cognitive Therapy (MBCT) for chronic pain (Day 2017).

Exclusion criteria (in addition to quantitative study criteria):

Non-completers (participants who completed less than 6/8 course sessions)

Declined to take part in interviews

SAMPLING

An opportunity sample from all patients invited to take part to the quantitative research aspect, invited as part of the initial quantitative study informed consent process.

We will invite all participants from the sample, aiming from 10-15 participants from each the stress and pain version of the courses, hence a total sample of 30 participants maximum and a target of 10 completed interviews for each intervention.

iv. Proposed method(s) of data analysis

Quantitative:

PRELIMINARY ANALYSIS

After randomisation, we will carry out preliminary baseline analysis using independent group t-tests to establish no significant demographic (age, education, duration of pain, number of comorbid medical conditions, visits for pain the past three months) or psychometric differences between the groups. This will act as a pseudo-waiting list treatment-as-usual (TAU) control group.

MAIN ANALYSIS

Treatment process change and outcomes

Means, Standard Deviations (SDs), between-group analysis of variance and co-variance (ANOVA, Between-Group ANCOVA) results and effect sizes (Between-Group effect sizes: d) for pretreatment, session-by session process change tracking including a practical selection of accepted and validated process-change measurement for all six areas of psychological flexibility and outcome measurement related to:

- pain intensity and interference
- impact on functioning
- emotional functioning (depression, pain catastrophizing)
- Global impression of functioning

for baseline, half-way, end-of-treatment and follow up

Analysis will be performed utilising SPSS.

These will include a practical selection of primary outcome measures, treatment process measures, as well as measures of emotional functioning, patient rating of change and change in medication use.

Post-hoc analysis

Will include number of GP and A&E visits comparing the waiting period and from the end of treatment to follow up.

STATISTICAL POWER

This study will be a modification of a previous pilot test trial of a brief, *widely inclusive* UK primary care setting (McCracken, Sato and Taylor, 2013), to include the whole sample of participants acting as a waiting list control, randomly allocated to two active treatment conditions. In line with this study which was delivered in a population area of 119,000 people, power calculations were not completed, nor were formal predictions of significant treatment effects. This was on the basis that the same treatment format and in a community based sample had not been tried before and demonstrated of successful recruitment of > 60 participants within a two-month period and reporting moderate effect sizes for the active condition. Given the whole island population of Jersey is estimated currently at 106,000, power calculations will not be provided in this study as the sample size was deemed appropriate in the previous that also cited

a number of studies with similar sample sizes and obtained from populations greater than Jersey.

PROCESS AND OUTCOME MEASURES

Process and outcome measurement has included consideration of factors such participants' burden, requirement for validated ACT and mindfulness groups process measurement (Day, Jensen et al. 2014, Day 2017, Feliu-Soler, Montesinos et al. 2018), relevant recommendations on measurement of outcome in chronic pain (Dworkin, Turk et al. 2005) and our current research team resources.

Ultimately, in attempting to have a clearly targeted study, we have been unable to have comprehensive quantitative measurement and the qualitative analysis will go some way to compensate for that.

Process measures:

In line with a recent review of validated and acceptable measures of psychological flexibility in chronic pain (Feliu-Soler, Montesinos et al. 2018) :

1) *Acceptance*

- a. The 7-item Acceptance and Action Questionnaire v.2 (AAQ-II, Bond *et.al*, 2011) will be utilised to measure the person's change in willingness to experience general unpleasant feelings and emotions that are not pain related (not to unfairly disadvantage the stress version of the course)
- b. *Pain Acceptance* The 8-item Chronic Pain Acceptance Questionnaire (Fish, McGuire et al. 2010)

2) *Contact with the Present Moment:* The Mindful Attention Awareness Scale (Brown and Ryan 2003) will be utilised.

3) *Self in context:* The Self Experience Questionnaire (Yu, McCracken et al. 2016)(SEQ, Yu, McCracken & Norton, 2016) will be utilised.

4) *Cognitive fusion:* the Cognitive Fusion Questionnaire (Gillander *et. al*, 2014)

5) *Values:* The Chronic Pain Values Inventory (McCracken and Yang 2006)

6) *Committed Action:* The 8-item Committed Action Questionnaire (McCracken, Chilcot et al. 2015)

Outcome measures:

Pain Intensity and interference on quality of life : the Brief Pain Inventory – Short Form (Tan, Jensen et al. 2004), numeric rating scale (NRS) on intensity (scale 0-10) including, worst, least

average (in the past week) and right now. BPI interference scale for impact on quality of life.

Emotional Functioning

a. *Pain related distress:* The Pain Catastrophizing Scale (Sullivan, Bishop et al. 1995)

b. *Depression:* The Beck Depression Inventory – Fast Screen (Poole, Bramwell et al. 2009)

Global Impression of Functioning: the Patient's Global Impression of Change (Guy 1976) will allow to consider perceived improvement and deterioration.

Qualitative:

DATA ANALYSIS

Transcribed data will be managed with NVivo software. All transcripts will be read and reread to ensure familiarity with the data. We will use thematic analysis (Braun and Clarke 2006) to identify recurring themes across the data and examine relationships between themes. The thematic analysis will be undertaken by two researchers independently coding for emerging themes and then comparing codes and themes.

TOPIC GUIDE

Do you have any previous experience in taking part in clinical trials or medical research?

I'm really interested in finding out what were your initial expectations and feelings about the mindfulness course?

What do you feel you have gained from attending the course?

What (if any) changes have you noticed in your health/quality of life? [probe for anything getting better or worse: health, emotional, physical, practical]

How do you feel the course has contributed to how you manage chronic pain?

This study has involved you doing some reading, meditation and practices in everyday life ('habit releasers'). Would you give me a sense as to whether you have managed to engage in these practices? [Ask about how long typically they have practiced daily formal meditation; are they still practising?; What has stuck and what hasn't?]

Is there anything else you would like to say about your experience of the course?

How do you feel the teacher contributed to your experience of the course?

What contribution do you feel the group has made to what you have learnt?

Since attending the course:

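### The eight-week wait is tied to recruitment in one sentence and to course start in another, and the two agree for few participants when six months of case identification feeds group courses

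*Combined protocol and SAP*

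**What the plan says.** Two sentences in section 2.iii (Study design) fix the start of the wait differently.

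- **Recruitment anchor.** The design paragraph that follows Confidentiality compares the two courses and "the waiting-list at recruitment time and 8-weeks post recruitment, coinciding with the start of treatment". It adds that the randomised sample "will act as a pseudo-waiting-list control for the eight-week waiting period ahead of the intervention".
- **Course-start anchor.** Participants and Data Collection says: "Once recruited, participants will be required to complete baseline outcome and process measures, 8-weeks ahead of beginning their 8-week course". It continues: "Randomisation will take place at this point to either the stress or the pain course". The assessment is repeated in week 1 of the course.

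The surrounding text bears on whether these can agree:

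- The Case Identification entry opens "Over a six months period".
- Procedure plans for "8-12 participants for each of four stress and pain courses", with 50 recruited and at least 30 per arm.
- Section 2.v expects stress and pain courses to run over the same eight weeks, two of each, at pre-agreed times.
- Post-hoc Analysis (section 2.iv) compares GP and A&E visits in the waiting period with those between end of treatment and follow-up.

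The plan gives no number of rounds, no start dates, no intake rule and no window around eight weeks.

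**The concern.** A group course has one start date, but its members are recruited on many dates. If baseline is done on recruitment, as the first sentence implies, an early recruit to a round waits longer than a late one. Recruitment plus eight weeks then falls at course start only for those who happened to join eight weeks beforehand.

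The wait is the trial's only untreated comparison, and the rationale presents it as a pseudo treatment-as-usual condition that improves on earlier research. If its length differs between people, change over the wait mixes different durations of natural course and regression to the mean. It also no longer matches the eight-week course in length. The visit comparison is exposed more directly, because a count grows with the time over which it is taken and the plan mentions no rate or person-time adjustment. None of this can be repaired after the data are in, beyond adjusting for whatever interval was recorded.

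**Working it through.** The eight weeks is a design constant, so there is no derived figure of the plan's own to reproduce. The check is how far the wait departs from eight weeks if baseline is taken at recruitment.

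**Inputs from the documents.** Intended wait 8 weeks; case identification six months, taken as 26 weeks; 100 participants; 8-12 per course; the cited pilot's pace of more than 60 recruits in two months (Statistical Power).

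**Assumptions, not in the documents.** The six months is the enrolment period. Accrual is even. Baseline is at recruitment. Recruitment of T weeks is split into W equal rounds, each starting 8 weeks after its last recruit.

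**Formulas.** Each round takes g = T/W weeks to recruit. The wait is then uniform from 8 to 8 + g, with mean 8 + g/2. The share waiting no more than one week beyond 8 is 1/g.

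**Pace.** Over six months: 100/26 = 3.85 people per week. At the pilot's pace, taking 60 in two months: 100/60 × 2 × 52/12 = 14.4 weeks.

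| T (weeks) | Rounds | g | Wait (weeks) | Mean | Within one week of 8 |
|---|---|---|---|---|---|
| 26 | 1 | 26 | 8-34 | 21 | 4% |
| 26 | 2 | 13 | 8-21 | 14.5 | 8% |
| 26 | 4 | 6.5 | 8-14.5 | 11.25 | 15% |
| 14.4 | 1 | 14.4 | 8-22.4 | 15.2 | 7% |
| 14.4 | 2 | 7.2 | 8-15.2 | 11.6 | 14% |
| 14.4 | 4 | 3.6 | 8-11.6 | 9.8 | 28% |

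**How many rounds?** Read as two stress and two pain courses at a time, one block holds 4 × 8 = 32 to 4 × 12 = 48 people, and two blocks hold 64 to 96. On that reading 100 people do not fit in one block, so the single-round rows need more parallel courses than section 2.v lists.

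**The other anchor.** If baseline is scheduled back from the course date, everyone waits 8 weeks. The variation moves to the gap between recruitment and baseline: 0-26 weeks with one round, 0-13 with two and 0-6.5 with four, for T = 26.

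**Visit counts.** Suppose the visit rate never changes, and read the three-month follow-up as 13 weeks after treatment ends. The ratio of follow-up visits to waiting-period visits is then 13 divided by the mean wait:

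- wait of 8 weeks: 13/8 = 1.63
- mean of 11.25: 13/11.25 = 1.16
- mean of 14.5: 13/14.5 = 0.90
- mean of 21: 13/21 = 0.62

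With no true change, raw counts would show anything from a 63% rise to a 38% fall, depending only on how long people waited. Even a uniform eight-week wait needs rates here.

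**The case against.** The strongest reply is that the plan already contains the right rule. Baseline is stated to be eight weeks ahead of the course. The phrase about being recruited can mean simply after recruitment, not on the day of it. The eight-week waiting period and the abstract's "placed on a time-set waiting list and then randomly allocated" fit that reading. **This stands**: an eight-week wait is achievable under the plan's own text. It does not remove the sentence that assesses the wait from recruitment, and a team following that sentence would get variable waits.

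A reader might also infer that courses start only once filled, so that eight weeks is impossible for most people. The documents do not support this. They give a group size, and section 2.v mentions pre-agreed times, which points towards scheduled dates. The argument needs only a common start date per group.

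Three further points stand in part:

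- Six months is given for case identification. That it equals the enrolment period is a reasonable reading but is not stated.
- The assessment is already repeated in week 1, so a score near the start of treatment will exist.
- The main analysis compares stress with pain. With random allocation and both courses run in the same rounds, wait lengths balance between arms in expectation, so that comparison is largely protected. The abstract places allocation after the wait while Participants and Data Collection places it at baseline. That should be reconciled as a separate matter.

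**Conclusion.** The point holds as a conflict between two anchors for one interval, in a plan with no round schedule or window to settle it. On the recruitment anchor, most participants miss eight weeks by more than a week in all six scenarios: between 4% and 28% fall within it. On the course-start anchor, all have eight weeks.

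The range of waits, from 8-34 weeks at the widest to 8-11.6 at the narrowest, rests on even accrual, baseline at recruitment and a start eight weeks after the last recruit. These are scenarios, not predictions. The damage is confined to the pseudo treatment-as-usual comparison and the visit comparison. It is worth correcting before recruitment because the untreated comparison depends on it and the correction is cheap.

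**What to change.** Delete the recruitment anchor and state the following in section 2.iii:

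- Consent and GP screening run continuously.
- All participants in a course round complete baseline in one fixed week, eight weeks before that round's scheduled start.
- The repeat assessment is immediately before session 1.
- People who consent later join the next round.
- The number of rounds and their dates are given, with a stated window around eight weeks.
- The actual number of days between the two assessments is recorded for each participant.

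In section 2.iv, analyse GP and A&E visits as rates per person-week over the time actually observed.

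The cost is a wording change and date-driven survey invitations. The downside is a gap between consent and baseline for early volunteers, so a brief eligibility re-check is needed at baseline. Fewer, larger rounds lengthen that gap.
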